#### 6.0 TRIAL DESIGN AND DESCRIPTION

[figure not shown]
# 6.1 Trial Design

The study is an investigator and subject blinded, sponsor unblinded, placebo-controlled clinical study progressively assessing independent cohorts of healthy subjects to continue evaluation of the safety, tolerability, and PK of escalating single doses (SD) and multiple doses (MD) of TAK-831, as either a suspension or T2 tablet formulation, at levels higher than those achieved in the initial single and multiple rising dose (SRD/MRD) Study TAK-831-1001.

Up to 6 cohorts will be run either singly or in parallel as non- cerebrospinal fluid (CSF) cohorts with plasma analysis or CSF cohorts with CSF analysis in addition to plasma analysis to assess TAK-831 exposure and levels in the central nervous system (CNS). After meeting all the selection criteria, there will be 8 subjects enrolled in each cohort. They will be randomized on Day 1 in a 1:3 ratio to receive placebo or TAK-831.

All cohorts will start with an initial, in-house SD period to include predose PD assessments on Day -1, Day 1 TAK-831 dosing, and a 48-hour in-house observation period with full PK collections. The SD PK collection and observation phase will be followed by 14 days of in-house MD.

In CSF cohorts, lumbar CSF samples will be collected through either a single lumbar puncture or an indwelling temporary catheter on 2 separate occasions. In CSF cohorts that use an indwelling temporary catheter on both occasions, the first collection will occur on Day 1, and the second on Day 16. In CSF cohorts where the pre-dose CSF sample is collected through a single lumbar puncture, the first CSF sample will be collected on Day -1 prior to the start of monitoring and the second collection will be obtained through use of an indwelling temporary catheter on Day 16. If an indwelling temporary catheter is being used, it will collect serial CSF samples for 24 hours.

Subjects in each cohort will be confined during dosing and be kept in the study unit for 24 hours after the last dose for non-CSF cohorts and 48 hours after catheter removal in CSF cohorts. The total confinement period in non-CSF cohorts will be 19 days (Day -2 to Day 17), 20 days in CSF cohorts where an indwelling temporary catheter is being used on Day 1 and Day 16 (confinement from Day -1 to Day 19); and 21 days in CSF cohorts where CSF is collected through a single predose lumbar puncture on Day -1 prior to the start of and through an indwelling catheter on Day 16 (confinement from Day -2 to Day 19). Follow-up assessments will occur on Day 30 (±2) for all cohorts. An exception to these minimum confinement periods will be made if a determination is made to evaluate QT/QTc intervals for additional single doses of TAK-831 in non-CSF cohorts based on the established tolerated dose range.

The Study Schematic and Schedule of Study Procedures are provided in Section 2.0 and Section 3.0, respectively.

(QD) formulation  750 mg single dose administered as a suspension of found to have acceptable tolerability in Study TAK-831-1001. The highest multiple dose level in study was 400 mg suspension.  Evaluate safety, tolerability, PK and PD effects of increased doses of TAK-831 administered as a suspension as tolerated up to the maximum expost defined below. Once this objective is met, possible additional doses and dose regimens (eg, BID, sing doses), with or without CSF collections and CSF is being collected through a single lumbar puncture), will be examined, pending PK-PD resured to the collected through a single lumbar puncture of the collected through a single lumbar puncture.  Tablet formulation T2		600 mg/day	Tablet	T2 tablet formulation at 600 mg is expected to deliver exposures comparable to 400 mg administered as a suspension. This exposure level demonstrated acceptable safety and tolerability with multiple dosing
(a)  4 (with CSF)  100 mg/day (a)  Tablet formulation T2  (a)  Tablet formulation T2  (b)  Tablet formulation T2  Tablet Tablet formulation T2  Tablet	2 (with CSF)		•	TAK-831-1001. The highest multiple dose level in that
formulation T2  (a)  formulation T2  defined below. Once this objective is met, possible additional doses and dose regimens (eg, BID, sing doses), with or without CSF collections and CSF is being collected through a single lumbar puncture), will be examined, pending PK-PD results to Cohorts 1 and 2.  5 (with CSF where Day -1 15 mg CSF is collected through a single lumbar puncture)  TBD (a)  Tablet formulation T2	3		Suspension	
CSF is collected through a single lumbar puncture)  TBD (a)  Tablet formulation T2	4 (with CSF)	0 ,		(in non-CSF cohorts or in CSF cohorts where Day -1 CSF is being collected through a single lumbar puncture), will be examined, pending PK-PD results of Cohorts 1 and 2.
formulation T2	CSF is collected through	15 mg	Suspension	CCI
or suspension	6	TBD (a)		

TBD=to be determined.

a) No selected dose will have exposures projected to exceed the study exposure limits or a maximum 2000 mg dose, whichever is lower.

Exposure levels in each cohort will be monitored closely and will not exceed exposures seen at the end of a 13-week repeat dose toxicity studies in monkeys (see Section 6.3.2).

Since, the highest dose tested in single rising dose portion of Study TAK-831-1001 was 750 mg administered as a suspension, all dose levels above 750 mg/day will be tested first in SD setting before MD in subsequent cohorts.

All decisions concerning dose escalation will be made by Takeda (at a minimum, the clinical science representative[s], quantitative clinical pharmacologist, study statistician and pharmacovigilance physician) and the principal investigator. The investigator and subjects will remain blinded throughout the study, but at the completion of each cohort, specific Takeda personnel listed in associated study documentation may be unblinded to analyze data considered necessary to determine subsequent doses and cohort management decisions. All data presentations prepared for discussions with the investigator and site staff will contain only blinded study data, except in the event that formal study unblinding procedures detailed in Protocol Section 8.1.5 have been followed and discussion of related data is required.

If agreement regarding a dose escalation decision cannot be reached between the principal investigator and Takeda, the study will be stopped.

Based on emerging safety and tolerability and PK data, the planned dose levels may be modified.

All adverse events reported during the Treatment Period, both within and across cohorts, up to the time of discharge will be evaluated to assess the need for subject and/or study termination in accordance with the prespecified criteria for discontinuation/termination (Section 6.5).

Following assessment of the adverse event data and predefined criteria for study termination, dose escalation may be interrupted/stopped if these criteria are met. Based on review of study data as outlined above, Takeda, in consultation with the principal investigator, will decide if and how it is appropriate for the study to proceed.

Dose escalation may be interrupted/stopped if:

- Exposures in any cohort exceed those observed at the top dose tested in the monkey toxicity study, that is, a mean  $C_{max}$  of 3680 ng/mL or a mean  $AUC_{24}$  of 35,700 hr\*ng/mL.
- The exposures reach the plasma exposure plateau in the 2 highest dose cohorts.
- One or more subjects in any single cohort or across more than 1 cohort experience an SAE or 2 severe or clinically significant AEs occur that are considered related to study drug.
- One or more subjects in any single cohort or across more than 1 cohort experience severe psychiatric symptoms, including any level of treatment-emergent suicidal ideation\* that are considered related to study drug.

[\*Treatment-emergent suicidality compared to Baseline, as measured by an increase in suicidal ideation or behavior category (on the C-SSRS) during treatment from the maximum suicidal ideation/behavior category at Baseline, or any suicidal ideation/behavior during treatment if there was none at Baseline].

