# 2.0 STUDY SCHEMATIC

Cohorts	Pretreatme	nt Period	nents (a)				
(up to 6 as		Check-in/	SD	Part			Follow-
needed)	Screening	Baseline	Treatment	Evaluation	MD Part	Study Exit	up (b)
Non-CSF (or	Days -28 to -3	Day -2	Day 1	Days 1 to 2	Days 3 to	Day 17 (non-CSF	Day 30
CSF cohorts					16	cohort) / Day 19	(±2)
that collect						(CSF cohort	
Day -1 CSF						where Day -1	
samples via a						CSF is collected	
single predose						via a single	
lumbar						predose lumbar	
puncture)						puncture)	
CSF	Days -28 to -2	Day -1	Day 1	Days 1 to 2	Days 3 to	Day 19	Day 30
		-		-	16	-	(±2)
		+		Confinem	ent	→	

CSF=cerebrospinal fluid, MD=multiple dose, PD=pharmacodynamic, PK=pharmacodynamic, SD=single dose.

a) TAK-831 dosing will be on Day 1 for SD and Days 3 through 16 for MD.

b) The Follow-up Visit will occur by telephone unless abnormal, clinically significant findings are observed upon discharge. In these cases, subjects may then be brought back to the clinic for re-evaluation per investigator's discretion.

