#### PD/BIOMARKER EVALUATIONS

CCI

CCI

AE=adverse event, anti-HCV=antibody to hepatitis C virus, BMI=body mass index, C-SSRS=Columbia–Suicide Severity Rating Scale, ECG=electrocardiogram, FSH=follicle-stimulating hormone, HbA1c=glycosylated hemoglobin, HBsAg=hepatitis B surface antigen, hCG=human chorionic gonadotropin, HIV=human immunodeficiency syndrome, PGx=pharmacogenomics, TSH=thyrotropin.

- (a) Study exit for non-CSF cohorts occurs on Day 17 and for CSF cohorts on Day 19.
- (b) At Early Termination, perform all procedures per Section 7.6.
- (c) The Follow-up Visit will occur by telephone on Day 30 (±2) unless abnormal, clinically significant findings are observed upon discharge. In these cases, subjects must be brought back to the clinic for re-evaluation per investigator's discretion. (X) is for optional procedure.
- (d) BMI will be calculated only at Screening.
- (e) Record all ongoing medications from Screening and throughout the study.
- (f) Vital signs (oral temperature, respiratory rate, pulse, and blood pressure) will be obtained at Screening, Check-in, Day 1, and Days 3 through 16 at predose (within 60 minutes before dosing) and at 1, 4, and 12 hours after the morning dose, and Study Exit/Early Termination and as appropriate at the Follow-up Visit. Day 2 vital signs should be collected approximately 24 hours after the Day 1 dose is administered. Pulse and blood pressure will be measured after 5 minutes supine and again at 1 and 3 minutes after standing for all scheduled time points, with exception of Day 1, Day 2, and Day 16 in cohorts where CSF collection is performed using an indwelling catheter, when only supine measurements will be taken.
- (g) Only for CSF cohorts: A neurological assessment and eye examination (ophthalmological assessment of the retina, fundoscopy) will be performed on Day -2 (baseline collection through single lumbar puncture), Day -1 (baseline collection through indwelling catheter) and Day 15.
- (h) Lumbar spine radiography (for CSF cohorts only) if one has not been performed within the past 12 months prior to the screening visit.
- (i) A standard 12-lead ECG (single) will be recorded at Screening, Check-in, Day 1 (predose [within 60 minutes prior to dosing], and at 1.5 hour postdose (morning dose), Day 16 (predose [within 60 minutes prior to dosing], and at 1 and 2 hours after morning dose, Day 10 (predose), and Study Exit/Early Termination and as appropriate at the Follow-up Visit.

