**Protocol Incorporating Amendment No. 02** 

- (k) The C-SSRS (Lifetime/Recent) will be administered at Screening; the C-SSRS (since last visit) will be administered at Check-in and at Study Exit/Early Termination.
- (l) Clinical laboratory tests (hematology, serum chemistry, and urinalysis) will be collected at Screening, Check-in, and after a 10-hour fast at predose on Days 1, 10, and at Study Exit/Early Termination and as appropriate at the Follow-up Visit.
- (m) For women only: A FSH level will be obtained on postmenopausal women at Screening only.
- (n) For women only: Serum hCG will be performed at Screening, Day -1, and Study Exit/Early Termination, and at the Follow-up Visit if the subject is brought back to the clinic for re-evaluation.
- (o) Hormone laboratory tests (prolactin, growth hormone, cortisol, and TSH) will be collected on Day 1 (before dosing, under fasted conditions and 3 hours postdose) and at Study Exit/Early Termination (morning values, under fasted conditions) and as appropriate at the Follow-up Visit.
- (p) One blood sample (6 mL) will be collected for DNA analysis before dosing on Day 1.
- (q) Blood samples (4 mL) for PK analyses will be collected on Day 1 (within 30 minutes before dosing) and at 0.5, 1, 1.5, 2, 4, 8, 12, 24, hours after the morning dose; on Day 10 (predose), Day 13 (predose), and on Day 16 at predose (within 30 minutes before dosing), and at 0.5, 1, 2, 4, 8, 12, 16, and 24 hours after the morning dose and at Early Termination.

CCI

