#### 4.3 Benefit/Risk Profile

There is no benefit to subjects in this clinical study.

The following risk mitigation measures will be implemented in this study with TAK-831. These measures are based on what is known about the mechanism of action of TAK-831, nonclinical data, and the 2 phase 1 studies conducted to date. Procedures may be added during the study if necessary based on evaluation of any additional clinical or nonclinical safety data.

- TAK-831 has been used in a prior single dose (up to 750 mg in oral suspension and 100 mg in tablet T1 formulation and 14 days multiple dose (up to 400 mg QD in oral suspension) study in healthy subjects (TAK-831-1001) with good safety and tolerability, as well as a single dose PET study (TAK-831-1003), and these studies have not resulted in a safety signal that would prevent additional studies. Additionally, a T2 tablet formulation is currently under assessment in a single dose food effect study (TAK-831-1004) that will contribute additional data to inform dose selection during the conduct of this study.
- Acute hypersensitivity/anaphylactic reactions to new chemical entities are always a possible risk in any clinical study. Appropriate procedures should be used to manage such possible risks.
- Study procedure—specific risks include issues relating to blood collection for safety assessment/PK and PD monitoring (venipuncture may cause bruising), and the placement of ECG pads, which may cause some local redness and/or erythema/itching.
- The risk of pain or discomfort at the site of CSF collection and the risk of headache in cohorts where CSF will be collected for PK and PD assessment. Severe headaches may require a blood patch procedure. There is a small risk of infection with indwelling catheters.
- The investigator has discretion to use his/her clinical judgment as to whether to allow a subject to proceed in the study or whether to unblind the subject in order to determine his/her treatment allocation.
- The C-SSRS will be administered to monitor emergent suicidality.

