#### 9.0 STUDY PROCEDURES

The following sections describe the study procedures and data to be collected as indicated in the Schedule of Study Procedures (Section 3.0). For each procedure, subjects are to be assessed by the same investigator or site personnel whenever possible. Please note that it may become necessary to perform the following procedures at unscheduled time periods, per the discretion of the investigator.

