## 10.2.8.2 Reporting AEs

At each study visit, the investigator will assess whether any subjective AEs have occurred. A neutral question, such as "How have you been feeling since your last visit?" may be asked. Subjects may report AEs occurring at any other time during the study. Subjects experiencing an SAE before the first exposure to investigational product must be monitored until the symptoms subside and any clinically relevant changes in laboratory values have returned to Baseline or there is a satisfactory explanation for the change. Nonserious AEs that begin before the first exposure to investigational product, related or unrelated to the study procedure, need not be followed-up for the purposes of the protocol.

All subjects experiencing AEs, whether considered associated with the use of the study medication or not, must be monitored until the symptoms subside and any clinically relevant changes in laboratory values have returned to Baseline or until there is a satisfactory explanation for the changes observed. All AEs will be documented in the AE page of the eCRF, whether or not the investigator concludes that the event is related to the drug treatment. The following information will be documented for each event:

- Event term.
- Start and end date and time.
- Pattern of AE (frequency).
- Severity/intensity.
- Causality (investigator's opinion of the causal relationship between the event and administration of study drug[s]).
- Action taken with trial drug.
- Outcome of event.
- Seriousness.

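### No C-SSRS is scheduled while subjects are being dosed; one reading before the Day 10 dose would be a cheap safety gain

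*Protocol*

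**What the plan says.** Protocol Section 4.3 lists the scale among the risk mitigation measures: "The C-SSRS will be administered to monitor emergent suicidality".

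Section 6.2 allows escalation to be interrupted or stopped if even one subject has drug-related severe psychiatric symptoms, which include treatment-emergent suicidal ideation at any level. The first limb of the definition is "an increase in suicidal ideation or behavior category (on the C-SSRS) during treatment", measured against the worst category at Baseline. The second limb is any ideation or behavior during treatment in a subject who had none at Baseline.

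On timing, Section 3.0 footnote (k) puts the lifetime/recent form at Screening and then says that "the C-SSRS (since last visit) will be administered at Check-in and at Study Exit/Early Termination". The schedule row agrees and has no mark on Days 1 to 16. Section 9.2.6 describes only the Screening administration.

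On dosing, the note to the Section 2.0 schematic says "TAK-831 dosing will be on Day 1 for SD and Days 3 through 16 for MD". Section 3.0 footnote (a) adds: "Study exit for non-CSF cohorts occurs on Day 17 and for CSF cohorts on Day 19".

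Other routes to detection exist. The schedule has an AE assessment every day from Day 1 to Day 16, and Section 10.2.8.2 says that at each visit "the investigator will assess whether any subjective AEs have occurred". Section 6.2 says that AEs "both within and across cohorts, up to the time of discharge will be evaluated to assess the need for subject and/or study termination". Section 9.0 notes that "it may become necessary to perform the following procedures at unscheduled time periods, per the discretion of the investigator".

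**The concern.** The protocol chose this scale as its monitor and tied a sensitive trigger, any level of ideation in one subject, to a change on it during treatment. Yet no reading is planned while treatment is being given.

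The protocol also provides for action inside a cohort and for the single subject: the AE review in Section 6.2, the within-cohort stopping rules in Section 6.5.5.1, and discontinuation under Sections 7.5 and 7.6. A first reading after Day 16 cannot lead to a withheld dose in that subject. It may also come too late for subjects in a cohort running alongside; Section 6.2 runs Cohorts 1 and 2 in parallel.

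The exposure is partly new. Earlier multiple dosing reached 400 mg of suspension daily (Section 6.3.2). Cohort 2 receives 800 mg, and later doses are capped at 2000 mg or the exposure limit, whichever is lower (Table 6.a). The subjects are healthy and have no prospect of benefit.

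**Working it through.** No power or sample-size formula applies. The check is a day count from the schedule.

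**Inputs.** Dosing days: Section 2.0. C-SSRS days: Section 3.0, schedule row and footnote (k). Check-in and exit days by cohort type: Sections 2.0, 3.0 and 6.1. There is no Day 0 (SAP Section 8.1.2).

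**Reproducing the plan's own figures.**
- Dosing days: Day 1 plus Days 3 to 16 = 1 + 14 = 15. This matches the treatment duration in Section 1.0.
- Confinement, counting both end days and no Day 0, is exit day minus check-in day: 17 − (−2) = 19; 19 − (−1) = 20; 19 − (−2) = 21. All three match Section 6.1.

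**Current schedule.** The elapsed gap from Check-in to exit is the confinement count minus 1.

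| Cohort type | Check-in to exit | Gap (days) | Last dose (Day 16) to exit | Dosing days before first postdose C-SSRS |
|---|---|---|---|---|
| Non-CSF | Day −2 to 17 | 19 − 1 = 18 | 1 day | 15 of 15 |
| CSF, Day 1 catheter | Day −1 to 19 | 20 − 1 = 19 | 3 days | 15 of 15 |
| CSF, Day −1 puncture | Day −2 to 19 | 21 − 1 = 20 | 3 days | 15 of 15 |

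On Days 1 to 16 there are 0 scheduled C-SSRS and 16 daily AE assessments.

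**With one C-SSRS before the Day 10 dose.** Dosing days already passed: Day 1 plus Days 3 to 9 = 1 + 7 = 8. Remaining: 15 − 8 = 7 (Days 10 to 16).

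| Cohort type | Check-in to Day 10 | Day 10 to exit | Longest gap |
|---|---|---|---|
| Non-CSF | 10 − (−2) − 1 = 11 | 17 − 10 = 7 | 11 |
| CSF, Day 1 catheter | 10 − (−1) − 1 = 10 | 19 − 10 = 9 | 10 |
| CSF, Day −1 puncture | 10 − (−2) − 1 = 11 | 19 − 10 = 9 | 11 |

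**With Day 2 as well.** One dosing day precedes the first postdose reading and 14 remain. The longest gap becomes 8 days (non-CSF) or 9 days (both CSF types).

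These are calendar counts. They show when the scale is given, not how many events it would find.

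**The case against.** The strongest reply is that the plan is coherent as written and that this is only a preference for more frequent testing.

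- The exit form asks about the time since the last visit, so it covers the dosing period. Section 6.2 unblinds and reviews data for the next dose when a cohort is complete, and the form is available by then. This stands.
- The second limb of the definition can be read as met by ideation reported as an AE. AEs are assessed daily, an unscheduled C-SSRS is allowed, and anyone who stops early is assessed at termination. This stands, but these routes need the subject to speak up, the investigator to suspect, or the subject to leave. The AE prompt in Section 10.2.8.2 is an optional neutral question.
- Subjects are confined throughout dosing. Exclusion 22 removes those judged at risk of suicide, with recent serious ideation or with suicidal behavior in the past 2 years. Earlier studies are described as well tolerated, and no AE of special interest is named. This makes events less likely, although some doses here exceed earlier ones.
- Section 4.3 lets procedures be added if safety data call for it. That is true, but it is a response to a signal rather than a means of finding the first one.
- A positive exit reading can still lead to care: it is taken before discharge, significant findings at discharge bring re-evaluation, and AEs are followed up. This stands. Only dose withholding is lost.
- Day 2 is awkward where a catheter was placed on Day 1, because the 24-hour CSF collection runs into it. This also stands.

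A reader might infer that the Section 6.2 rule cannot be applied, or that suicidality goes unwatched during dosing. The documents support neither. The look-back form feeds the rule, and daily AE assessment with discretionary testing covers the dosing period.

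**Conclusion.** The point holds as a modest safety improvement that should be made; it is not a defect that disables the stopping rule. For a subject who completes the planned regimen, all 15 dosing days pass before the first scheduled postdose C-SSRS, with 18, 19 or 20 days between the Check-in and exit readings. The consequence is confined to ideation that is neither volunteered nor suspected during dosing. For that, the plan gives up the chance to withhold remaining doses, in that subject or possibly in a parallel cohort.

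The conclusion assumes that footnote (k) is the full C-SSRS schedule and that dosing runs as planned, since Section 6.4 allows its duration to change. The effect on a parallel cohort depends on relative start dates, which the documents do not give. They also give no rate of unvolunteered ideation, so no expected number of missed or late-detected cases can be stated. The schedule facts and day counts are certain; the clinical yield is not.

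**What to change.** Add the since-last-visit C-SSRS before the Day 10 dose in the Section 3.0 schedule row, footnote (k) and Section 9.2.6. Day 10 already carries a predose safety ECG, laboratory tests and vital signs. Add a sentence to Sections 7.5/7.6 saying that the investigator reviews a positive result before that subject's next dose, and that the result goes to the Section 6.2 escalation review. A Day 2 reading is optional and best left out in Day 1 catheter cohorts.

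The cost is one short questionnaire per subject, given in-house by raters already needed at Check-in and exit, with no new staff, visit or invasive procedure. It does need a protocol amendment with IRB/IEC handling, because timing changes to safety procedures under Section 6.4 may not increase the number of procedures per subject. SAP Section 8.11.6 only lists C-SSRS data, so the extra reading fits there without a new analysis.
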